### 9.1.2 Subject disposition

Patient disposition will be determined using information collected in the following CRF forms:

- Withdrawal Form (v2)
- Withdrawal from Trial Form (v3)
- Withdrawal from Protocolised Treatment Form (v3)
- Death Form
- End of Trial Form.

The Withdrawal Form v2 in version 2.0 of the CRF was superseded by two new forms (Withdrawal from Protocolised Treatment v3 and Withdrawal from Trial Form v3 ) in version 3.0 of the CRF, approved 16 Dec 2015. This allowed a clearer distinction between those patients discontinuing protocolised treatment, who remain under long term follow up, and those withdrawing from the trial completely, who have no further data collected.

Table 3 lists the criteria used to reconcile the two types of withdrawal forms, based on the reason of discontinuation given in v2 of the form. V3 criteria will be used in the report.

When either “Investigator decision” or “Other” was selected in the v2 form, sites were asked to confirm whether the patient was withdrawn from study or from protocolised treatment by adding the text “STUDY” or “PROTOCOL” respectively in the relevant “Please Specify” text box.

When “Participant decision” was selected, sites were asked to confirm that this indeed meant the patient withdrew consent to further participation in the study, or otherwise to reclassify the withdrawal reason as “Other” and add “PROTOCOL” in the relevant text box.

Table 3: Withdrawal forms harmony

[figure not shown]
V2		V3	
Withdrawal		Withdrawal from Study	Withdrawal from Protocolised Treatment
WDReason	Text box	WDRea1	WDPRO2
1-Not in Remission at Month 4			1-Not in Remission at Month 4
2-Participant decision		2-Withdrawal of consent	
3-Investigator decision	"STUDY"	3-Other	3-Investigator decision
	"PROTOCOL"		
4-Relapse			2-Relapse
5-Death		1-Death	
6-Other	"STUDY"	3-Other	4-Other
	"PROTOCOL"		

Data management will check each form to ensure consistency and completeness across all the forms.

9.1.3 CONSORT diagram

A CONSORT diagram (Figure 2) will be presented to show patient disposition within the study.

Figure 2: Example CONSORT diagram for the trial

 Patients not eligible for randomisation remain under long-term follow up, unless they withdraw consent.

 The full analysis population includes all randomised patients, including those subsequently withdrawn.

## 9.2 Derived variables

The following derived variables will be calculated from source variables recoded in MACRO:

### 1. Baseline Medical History

- **Prior disease duration (years)** – calculated from the date of diagnosis to the date of screening. First day of the month/year will be used for fuzzy dates. Date difference in years will be rounded to 1 decimal figure.
- **Historical ANCA positivity (Positive both/anti-PR3/anti-MPO, Negative, Missing)** – a categorical variable, calculated from variables in the Enrolment Form recording historical positivity to anti-PR3 and anti-MPO ANCA. Calculated according to the following rules (if only one value is confirmed and the other is missing, the missing one is assumed to be negative):

**Table 4: Historical ANCA positivity**

		Anti-MPO	
		Positive	Negative
Anti-PR3	Positive	Positive for both anti-PR3 & anti-MPO	Positive for anti-PR3
	Negative	Positive for anti-MPO	Negative

- **Total number of Body Systems affected (integer)** – a count of the number of organ manifestations reported in the Baseline Medical History Form (max count = 11). The variable will be reported both as categorical and continuous.

### 2. Prior treatment

- **Cyclophosphamide (Yes/No)** – categorical variable determining whether subjects have ever received any cyclophosphamide treatment, either IV or oral. Calculated from oral and IV cyclophosphamide variables; patients can receive either treatment or both. In incomplete cases the subject will be regarded as not having received the treatment specified.
- **Cumulative cyclophosphamide dose (g)** – continuous variable, sum of the Oral and IV cyclophosphamide doses (g); patients can receive either

treatment or both. In incomplete cases the subject will be regarded as not having received the treatment specified (i.e. dose = 0 g).

- **Rituximab or cyclophosphamide (Yes/No)** – categorical variable determining whether subjects have ever received any rituximab or cyclophosphamide treatment, either IV or oral. Calculated rituximab and cyclophosphamide variables; patients can receive either treatment or both. In incomplete cases the subject will be regarded as not having received the treatment specified.
- **Number of prior immunosuppressants (excluding glucocorticoids) (integer)** – a count of the number of prior immunosuppressants (excluding glucocorticoids) received by each subject. The following treatments are included: cyclophosphamide (Oral or IV), rituximab, azathioprine, methotrexate, mycophenolate mofetil, IVIG, anti-TNFs, and other immunosuppression listed in the Baseline Medical History Form. In incomplete cases the subject will be regarded as not having received the treatment specified. The variable will be reported both as categorical and continuous.

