## 8.5 Missing Data

(ICH E3; 9.7.1, 11.4.2.2. ICH E9; 5.3. EMA Guideline on Missing Data in Confirmatory Clinical Trials)

The sample size of non-missing values will be reported for summary tables. It is expected that the incidence of missing data will be low. Missing data will be assumed to be missing at random. In practice, missing values will be ignored for calculation of summary statistics. The number of non-missing values will be reported and used instead of the population or subgroup size as a denominator as needed. The overall size of the population, including missing values will be reported within the title of the table or figure to convey the amount of missing data.

Due to logistic reasons, the PROMIS questionnaire was not administered to the full study population. The number of sites and patients not taking part will be noted.

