**Table 5: ANCA Status**

		Anti-MPO		
		Positive	Negative	Not measured
Anti-PR3	Positive	Positive PR3 & MPO	Positive PR3	Positive PR3
	Negative	Positive MPO	Negative	Unknown
	Not measured	Positive MPO	Unknown	Unknown

Table 6: Details of formulas for derived variables

Variable name	Label	Type	Original variables (MACRO ShortCode)	Formula
MHDuration	Prior disease duration	Real	MHDat1, Visit1	Date difference (years)
HisANCA	Historical ANCA positivity	Category	MHEli1, MHEli2	See Table 4 for details
BLM_Score BLM_Score_cat	Total number of Body Systems affected	Integer/ Category	BLM_* variables	Sum
MHCycl	Total cyclophosphamide	Category	MHTre3, MHTre4	if either = 1 then => 1 (Yes) else => 0 (No)
MHCyclDose	Cumulative cyclophosphamide dose	Real	MHCyc1, MHIVC1	Sum
MHRitCyc	Previous treatment with rituximab or cyclophosphamide (either IV or oral)	Category	MHTre5, MHCycl	if either = 1 then => 1 (Yes) else => 0 (No)
MHImmN MHImmN_cat	Number of prior immunosuppressants	Integer/ Category	CumCyclo, MHTre5, MHTre6, MHTre7, MHTre8, MHTre11, MHTre12, MHImS1, MHImS2, MHImS3, MHImS4, MHImS5, MHImS6	Sum
BVASStatus	Disease status	Category	BVAS12a, BVAS12b, BVAS12c, BVAS12d	Hierarchical order, categories evaluated in order, from the most specific to the most general: 1. Remission 2. Severe flare 3. Limited flare 4. Persistent
CDAScore CDAScore_cat CDAScore_grp	Total CDA score	Integer/ Category	selected variables of CDA Form (see section 9.8)	Sum
CDADiff CDADiff_cat	Change in total CDA score between month 4 and month 12, month 24, month 36 & month 48. Change in total CDA score between	Integer/ Category	CDAScore	Difference

	month 24 and month 36 & month 48			
TreatRituxSum	Total rituximab dose (mg)	Real	TreatTotalRitux	Sum
TreatRituxPrctcol	Overall full rituximab treatment	Category	TreatAdmnProtcol	Yes if sum(TreatAdminProtocol="Yes")=5
TreatRituxMonths	Number of full rituximab infusions	Integer/Category	TreatAdmnProtcol	count(TreatAdminProtocol="Yes")
TreatMPredDose	Total IV methylpredniso(lo)ne dose (mg)	Real	TreatMPredDose	Sum
PredMean PredMean24	Average predniso(lo)ne dose (mg/day) - (Overall /Maintenance)	Real	FUp1aPredDose	Average If FUp1a1 then Fu1aPredDose=0
PredAUC PredAUC24	AUC of predniso(lo)ne dose (mg) - (Overall /Maintenance)	Real	FUp1aPredDose	Vertical step function, assumes month=30days

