### 11.3 Hypogammaglobulinemia

Hypogammaglobulinemia is defined as a value of IgG < 5 g/L measured at any stage of the trial (including visits occurring during the induction period). Frequency tables for hypogammaglobulinemia will be reported using the full analysis population and stratified by treatment arm and:

- a) Induction regimen (1A/1B)
- b) ANCA type (anti-PR3/anti-MPO)
- c) Relapse type (Severe/Non severe)
- d) Previous treatment with rituximab (Yes/No)
- e) Previous treatment with cyclophosphamide (Yes/No)
- f) Previous treatment with rituximab or cyclophosphamide (Yes/No)
- g) Baseline (Screening/Month 0) IgG (g/L).

A logistic regression analysis will be carried out to predict hypogammaglobulinemia, using the above as predictor variables. Individual univariate models and a multivariate model will be considered. Outcomes (Estimate, 95% CI and P-value) will be surmised in tabular form.

These analysis are to be considered exploratory only, as they were not specified in the protocol and the data is observational.

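### SAP 9.2 codes incomplete prior-treatment records as not received and missing cyclophosphamide dose as 0 g, an unexplained departure from SAP 8.5 that can only understate prior exposure

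*SAP*

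**What the plan says.** SAP section 9.2, item 2, defines four derived prior-treatment variables: cyclophosphamide (Yes/No), cumulative cyclophosphamide dose, rituximab or cyclophosphamide (Yes/No), and the number of prior immunosuppressants. All four carry the sentence "In incomplete cases the subject will be regarded as not having received the treatment specified". For dose, the SAP adds that this means 0 g: "In incomplete cases the subject will be regarded as not having received the treatment specified (i.e. dose = 0 g".

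SAP Table 6 gives the formula for both flags: "if either = 1 then => 1 (Yes) else => 0 (No". Anything other than a recorded 1, including a blank, therefore becomes No. Cumulative dose is a plain sum of the oral and IV dose fields.

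The general rule is in SAP 8.5: "In practice, missing values will be ignored for calculation of summary statistics", and "The number of non-missing values will be reported and used instead of the population or subgroup size as a denominator as needed". The same section states "Missing data will be assumed to be missing at random" and expects missing data to be infrequent, without giving a figure.

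SAP 9.6.1 tabulates the prior-treatment items and doses. SAP 11.3 lists "Previous treatment with cyclophosphamide (Yes/No") and the rituximab-or-cyclophosphamide flag among the predictors in logistic models for IgG below 5 g/L. It labels those models exploratory.

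**The concern.** Not recorded and not received are different states, and the 9.2 rule merges them. The error runs one way. A missing field can turn a true Yes into No, or a true dose into 0 g or a partial sum, but it cannot do the reverse. The derived variable then looks complete for every patient.

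Two outputs are exposed. The first is the baseline table, where cumulative cyclophosphamide dose describes how heavily treated the population was and whether the arms are balanced. The second is the hypogammaglobulinaemia model, where false No values would mix exposed patients into the reference group and shrink a single-predictor odds ratio towards 1.

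The rule can also produce records that contradict each other. Flag and dose come from different fields, so a patient can be Yes with 0 g. Inclusion criterion 4 requires earlier induction with an immunosuppressant, yet an eligible patient with an incomplete history could be counted as having had none.

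**Working it through.** The plan states no missingness, exposure prevalence or odds ratio for these variables, so there is no figure of its own to reproduce. The check has two parts.

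**1. Which records go wrong**

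| Record | Derived flag | Derived dose |
|---|---|---|
| One route Yes, its dose missing, other route No | Yes (correct) | 0 g (too low) |
| Both routes Yes, one dose missing | Yes (correct) | partial sum (too low), or 0 g if the rule applies to the total |
| No route Yes, one route unknown and in fact given | No (wrong) | 0 g (too low) |
| No route Yes, one route unknown and not given | No (correct by chance) | 0 g (correct by chance) |

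The text does not say whether 0 g applies to the missing route or to the total. A missing dose alone never misclassifies the flag. Dose is not a predictor in SAP 11.3, so the dose problem stays in the baseline tables.

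**2. How large the effect could be**

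All inputs are assumptions except the planned 160 randomised patients (SAP section 7). Let *p* be the true exposure prevalence and *m* the fraction of patients with unknown status, independent of exposure and outcome. The risk in the unexposed is 0.15 and the true odds ratio is 2.0.

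- Risk in the exposed: odds = 2 × 0.15/0.85 = 0.353, so risk = 0.353/1.353 = 0.261.
- Coded prevalence = *p*(1 − *m*).
- Share of the coded-No group that was really exposed: *w* = *pm*/[(1 − *p*) + *pm*].
- Risk in the coded-No group = 0.261*w* + 0.15(1 − *w*).
- Observed odds ratio = 0.353 divided by the odds in the coded-No group.

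Worked case, *p* = 0.6 and *m* = 0.10: *w* = 0.06/0.46 = 0.13; risk = 0.261 × 0.13 + 0.15 × 0.87 = 0.164; odds = 0.197; odds ratio = 0.353/0.197 = 1.79.

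| *m* | Patients of 160 | Coded prevalence (true 60%) | Odds ratio (true 2.00) |
|---|---|---|---|
| 2% | 3 | 58.8% | 1.95 |
| 5% | 8 | 57.0% | 1.88 |
| 10% | 16 | 54.0% | 1.79 |
| 20% | 32 | 48.0% | 1.66 |

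Over *p* = 40–80%, the odds ratio is 1.98 to 1.74 at 2–5% missing. The lowest value in the grid is 1.42, at 80% exposed and 20% missing. If unknown status is left missing, the expected prevalence is *p* and the odds ratio stays at 2.00 under the same assumptions.

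For dose, if a fraction *m* of treated patients enters as 0 g, the mean among the treated is multiplied by (1 − *m*). An assumed true mean of 15 g becomes 14.7 g at 2%, 14.25 g at 5%, 13.5 g at 10% and 12 g at 20%.

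**The case against.** The strongest reply is that 9.2 is a deliberate, written exception. The opening of SAP section 9 says that departures from its overview will be noted in its sub-sections, and this is one. That stands. A reader might infer that 9.2 and 8.5 contradict each other, but a specific rule under a general one is a choice. What remains open to criticism is that no reason and no sensitivity analysis accompany it.

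A reader might also infer that the rule hides missingness altogether. It does not. SAP 9.6.1 reports oral cyclophosphamide, IV cyclophosphamide, rituximab and the separate doses as items in their own right, and section 9 requires the non-missing number for each. The derived variables lose that information, but the component rows keep it.

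A third tempting reading is that a predictor in the IgG model is misclassified as a matter of fact. The documents support only a conditional statement, because one recorded Yes is enough for Yes. Stand-alone prior rituximab, also a predictor, is not covered by the rule.

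Nothing in the documents supports missingness of 10–20%. SAP 8.5 expects it to be low, SAP 6.4 describes routine queries for missing forms, and prior cyclophosphamide exposure is a named baseline item in protocol 12.2.

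The SAP's practice elsewhere is mixed. In 9.2, average prednisolone dose takes 0 only for an explicit No and ignores missing values, which is the distinction sought here. The prednisolone area under the curve sets missing to 0.

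**Conclusion.** The point holds as a minor one. The 9.2 rule can only understate prior exposure, and it does so for cumulative cyclophosphamide dose whenever a treated patient has no recorded dose. For the two flags, the error needs no component recorded Yes and a missing one that was given.

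The size rests on missingness that the documents do not report. With no missing data there is no bias. At 2–5% missing the single-predictor odds ratio moves from 2.0 to 1.95–1.88 under the stated assumptions; the 10–20% figures of 1.79–1.66 show the upper end and are not a forecast. Attenuation towards 1 is shown only for a single predictor with error unrelated to outcome. The multivariate model holds prior rituximab, prior cyclophosphamide and their composite together, so the direction there is not established.

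The consequences stop at descriptive baseline tables and an exploratory model. The primary Cox model adjusts only for the three stratification factors and is unaffected.

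**What to change.** In SAP 9.2 item 2 and Table 6:

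- **Dose.** Set cumulative dose to missing when treatment is Yes and the dose is not recorded. Use 0 g only for a recorded No.
- **Flags.** Set each of the two Yes/No flags to missing when no component is Yes and at least one is unknown. Keep Yes whenever any component is Yes.
- **Reporting.** Give the number unknown by arm beside each derived variable, in line with 8.5. The current rule may be kept as a sensitivity analysis.
- **Count of prior immunosuppressants.** Apply the missing rule only to the named Yes/No treatment items, and treat blank slots for other immunosuppression as none. Table 6 sums six fields (MHImS1 to MHImS6) that appear to be such slots, although the CRF is not among the documents. Treating blanks there as missing could remove the count for most patients.

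The cost is a few words of SAP text, a small change to the derivation code and slightly smaller denominators.

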### 3. Disease Activity (BVAS/WG)

- **BVAS/WG status (categorical)** – Disease status is determined from section 12 of the BVAS/WG form. At any given visit each patient is assigned a current disease status: "Severe flare/new disease", "Limited flare/new disease", "Persistent disease", "Remission". If multiple statuses are selected on the form a hierarchical classification is employed: "Remission" excludes all others, "Severe flare/new" trumps "Limited flare/new" and "Persistent" is trumped by all others. The data manager is responsible for the consistency of the data & raises queries accordingly (in particular it is expected that "Remission" be mutually exclusive of all other selections).

### 4. Disease related assessment (CDA)

- **Total CDA score (integer)** – Accrual of damage as measured by the combined damage assessment (CDA) score. Each persistent or new occurrence of damage is recorded as "Yes" and given a score of 1. The cumulative accrual of damage is obtained by summing across the

different types of damage to get an overall score (max score = 64). The variable will be reported both as categorical and continuous.

- **Change in total CDA score between month 4 and month 12 (integer)** – difference in Total CDA score between month 4 (randomisation) and month 12, calculated for complete–case records only. The variable will be reported both as categorical and continuous.
- **Change in total CDA score between month 4 and month 24 (integer)** – difference in Total CDA score between month 4 (randomisation) and month 24, calculated for complete–case records only. The variable will be reported both as categorical and continuous.
- **Change in total CDA score between month 4 and month 36 (integer)** – difference in Total CDA score between month 4 (randomisation) and month 36, calculated for complete–case records only. The variable will be reported both as categorical and continuous.
- **Change in total CDA score between month 4 and month 48 (integer)** – difference in Total CDA score between month 4 (randomisation) and month 48, calculated for complete–case records only. The variable will be reported both as categorical and continuous.
- **Change in total CDA score between month 24 and month 36 (integer)** – difference in Total CDA score between month 24 (end of maintenance treatment) and month 36, calculated for complete–case records only. The variable will be reported both as categorical and continuous.
- **Change in total CDA score between month 24 and month 48 (integer)** – difference in Total CDA score between month 24 (end of maintenance treatment) and month 48, calculated for complete–case records only. The variable will be reported both as categorical and continuous.

## 5. Treatment Exposure (Treatment Form)

---

 A different scoring system from the one used in the Induction phase report is employed. This new scoring system is based on COMBIVAS's VDI (Vasculitis Damage Index) form. The new scoring system has a maximum score of 64, compared to the Induction phase report one that had a maximum score of 110. For comparison new CDA scores for the Induction phase months (visits Month 0 and Month 4) will be included in this report. Further details on how the CDA score is computed can be found in section 9.8.

- **Total maintenance rituximab dose (mg)** – cumulative rituximab dose across the maintenance phase of treatment only, from the Treatment Form of months 4, 8, 12, 16 and 20. Missing data (due to early withdrawal or any other reason –e.g. missing form) will be ignored (i.e. it's assumed no treatment was given, 0 mg).
- **Overall full rituximab treatment – maintenance (Yes/No)** – categorical variable, determining whether the subject has received all five full rituximab infusions as per protocol. Subjects are assumed to have followed protocol unless deviations were explicitly recorded in the Treatment form (i.e. "Treat6" = 1), any recorded deviation is considered an overall non-compliance, while missing forms are ignored.
- **Number of full rituximab infusions administered (integer)** – calculated across the maintenance phase of treatment, from the Treatment form of month 4,8,12,16 and 20. Counts explicitly the number of months when rituximab treatment was administered according to protocol. Thus "3 doses" would mean that 3 infusions administered were given as per protocol. Missing forms (NA) are ignored.
- **Total maintenance IV methylpredniso(lo)ne dose (mg)** – cumulative IV methylpredniso(lo)ne dose across the maintenance phase of treatment only, from the Treatment form. Missing data (due to early withdrawal or any other reason –e.g. missing form) will be ignored (i.e. it's assumed no treatment was give, 0 mg).

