#### Maintenance Phase:

Neither RITUXVAS nor RAVE addressed the question of repeat dosing with rituximab as a maintenance strategy. The two largest data sets presently available utilising repeat rituximab as a maintenance strategy, employed doses of 1000mg x 2 every 6 months (Mayo Clinic) (total 8000mg in 24 months) or 1000mg every 6 months (Cambridge, UK) (total 4000mg in 24 months). The selected dose for RITAZAREM, 1000mg every 4 months (5000mg in total), falls between these two regimens. In addition, 9 out of 10 relapses seen in the Cambridge cohort occurred in the 2 months prior to a scheduled rituximab dose, yet responded to further rituximab. Reducing the interval between rituximab doses to 4 months has the potential to further reduce relapse rates.

B cell depletion is a pharmacodynamic surrogate for rituximab efficacy. Because B cell return typically commences after four months, by reducing the dosing interval to four months the study aims to maintain 100% B cell depletion for the 24 month treatment phase.

No data exists for a total rituximab dose below 1000mg in vasculitis. Adopting a 375mg/m^2 dose every 4 months as a maintenance strategy would result in a median dose of 700mg. The MAINRITSAN study is employing a 500mg dose every 6 months. This is likely to result in under dosing, because 20% of patients relapsed using 1000mg every 6 months in the Cambridge cohort. In addition, more frequent maintenance dosing is inconvenient for patients and more expensive.

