#### Rituximab maintenance group

Rituximab 1000 mg x 1 dose at months 4, 8, 12, 16 and 20 and glucocorticoids.

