#### 6. Treatment exposure (Follow Up Form)

- **Average predniso(lo)ne dose (mg/day)** – average predniso(lo)ne dose, from randomisation to the end of trial, using the most recent daily dose as recorded in the Follow Up form at month 4, 8, 12, 16, 20, 24, 27, 30, 36, 42, and 48. If predniso(lo)ne treatment was explicitly recorded as not given in the Follow Up Form (i.e. FUp1a1 = "No") then a dose = 0 mg/day will be implied, while missing data (due to early withdrawal or any other reason –e.g. missing form) will be ignored.

---

 A separate variable in the Follow Up form reports cumulative rituximab dose at 24 months, which includes doses administered during the induction phase.

 A separate variable in the Follow Up form reports cumulative IV methylpredniso(lo)ne dose at 24 months, which includes doses administered during the induction phase

- **Average predniso(lo)ne dose (mg/day) in the maintenance phase** – as above but calculated using the most recent daily dose as recorded in the Follow Up form at month 4, 8, 12, 16, 20, and 24 only.
- **AUC of predniso(lo)ne dose (mg)** – Area under the curve of predniso(lo)ne dose, calculated using the most recent daily dose as recorded in the Follow Up form at month 4, 8, 12, 16, 20, 24, 27, 30, 36, 42, and 48 employing a vertical step function and assuming a month to be 30 days. Missing data will be assumed to have a value of 0 mg/day.
- **AUC of predniso(lo)ne dose (mg) in the maintenance phase** – as above but calculated using the most recent daily dose as recorded in the Follow Up form at month 4, 8, 12, 16, 20, and 24 only.
- **Average azathioprine dose (mg/day)** – average azathioprine dose, from randomisation to the end of trial, using the most recent daily dose as recorded in the Follow Up form at month 4, 8, 12, 16, 20, 24, 27, 30, 36, 42, and 48. Missing data (due to early withdrawal or any other reason – e.g. missing form) will be ignored.
- **Average azathioprine dose (mg/day) in the maintenance phase** – as above but calculated using the most recent daily dose as recorded in the Follow Up form at month 4, 8, 12, 16, 20, and 24 only.
- **Average methotrexate dose (mg/week)** – average methotrexate dose, from randomisation to the end of trial, using the most recent daily dose as recorded in the Follow Up form at month 4, 8, 12, 16, 20, 24, 27, 30, 36, 42, and 48. Missing data (due to early withdrawal or any other reason –e.g. missing form) will be ignored.

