### 9.10.1 Rituximab treatment

---

 See *Medication Compliance.docx*

 See section 11.2 of the protocol for further details of azathioprine administration.

The Treatment form records details of rituximab treatment, at months 4, 8, 12, 16 and 20, as recorded by the PI. The form will be reported at each time point using the full analysis population. The following variables will be summarised in accordance with section 9:

- Rituximab dose (mg)
- Rituximab administered according to protocol (Yes/No)
- Reasons for non-compliance, counts:
  - a) Rituximab not administered as IgG < 3g/L
  - b) Incomplete
  - c) Interrupted
  - d) Other

Reasons given for incomplete/interrupted/other treatment non-compliance will be listed per patient, per visit.

In addition, total cumulative rituximab dose after 24 months as recorded in the Follow Up form as well as the following derived variable (details in section 9.2) will be calculated across the maintenance therapy period and summarised in accordance with section 9:

- Cumulative rituximab dose (mg) up to 24 months
- Total rituximab dose in maintenance phase (mg) – derived variable, details in section 9.2
- Overall full rituximab treatment (Yes/No) – derived variable, details in section 9.2
- Number of full rituximab infusions – derived variable, details in section 9.2

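### A missing Treatment Form is scored 0 mg in the maintenance rituximab and IV methylprednisolone totals, so a dose given but not recorded counts as not given

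*SAP*

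**What the plan says.** SAP 9.2, item 5, derives two maintenance totals from the Treatment Form. For rituximab, the rule on absent data is "missing form) will be ignored (i.e. it's assumed no treatment was given, 0 mg". For IV methylprednisolone it is "missing form) will be ignored (i.e. it's assumed no treatment was give, 0 mg". Both rules cover early withdrawal and every other cause of a gap.

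For the variable on overall full rituximab treatment, the same item presumes that the protocol was followed unless the form shows otherwise: "any recorded deviation is considered an overall non-compliance, while missing forms are ignored". SAP Table 6 defines that variable differently, as Yes only when five administrations are recorded as per protocol.

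SAP 9.10.1 describes the source: "The Treatment form records details of rituximab treatment, at months 4, 8, 12, 16 and 20, as recorded by the PI". SAP Table 2 schedules the form at months 0, 4, 8, 12, 16 and 20, with no mark at unscheduled visits and no restriction to one arm.

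There is a second source. A footnote to SAP 9.2 states: "A separate variable in the Follow Up form reports cumulative rituximab dose at 24 months, which includes doses administered during the induction phase". A matching footnote covers IV methylprednisolone. SAP 9.10.1 and 9.10.2 list both cumulative doses next to the derived totals.

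The general rule in SAP 8.5 is "The number of non-missing values will be reported and used instead of the population or subgroup size as a denominator as needed".

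**The concern.** The rule gives the same value to two different states: no dose was given (a true 0 mg), and no form is available (dose unknown). The error can go only one way, towards understated exposure. Because the gap is replaced by a number, the patient's total counts as observed, so the non-missing count that SAP 8.5 relies on does not show how many totals are affected.

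The SAP draws the distinction elsewhere. For average prednisolone (SAP 9.2, item 6), 0 mg/day is used only when the form explicitly records that the drug was not given, and missing forms are left out.

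Two results depend on these totals. Rituximab exposure is the background to the secondary objective on long-term safety. Cumulative glucocorticoid exposure is a listed secondary endpoint. SAP 10.2 plans no analysis for it, so the descriptive summaries in 9.10.2 are where it will be read. For IV steroid there is a further gap: the only form that feeds the total is not scheduled at the visits where a relapse is assessed.

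**Working it through.** **Inputs.** Maintenance rituximab: "Rituximab 1000 mg x 1 dose at months 4, 8, 12, 16 and 20 and glucocorticoids" (Protocol 11.1.1). Pre-medication: 100 mg IV methylprednisolone before each maintenance dose (Protocol 11.1.1). The number of missing Treatment Forms is not given, so a range is assumed.

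**1. The plan's own total.** 5 × 1000 mg = 5000 mg. This agrees with Protocol 11.1, "1000mg every 4 months (5000mg in total", and with the 5 g maximum in Protocol 11.1.3. Planned pre-medication is 5 × 100 mg = 500 mg.

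**2. One patient, all five infusions given, k forms missing.** Scored rituximab = (5 − k) × 1000 mg; scored IV methylprednisolone = (5 − k) × 100 mg.
- k = 1: 4000 mg and 400 mg (20% too low)
- k = 2: 3000 mg and 300 mg (40% too low)

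**3. Rituximab arm mean.** Assume that every patient receives all five infusions and that a fraction m of given infusions has no form. Scored means are 5000(1 − m) and 500(1 − m). With independent losses, the share of patients with at least one affected form is 1 − (1 − m)^5.

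| m (assumed) | Rituximab mean | Shortfall | IV methylprednisolone mean | Shortfall | Patients affected |
|---|---|---|---|---|---|
| 1% | 4950 mg | 50 mg | 495 mg | 5 mg | 4.9% |
| 5% | 4750 mg | 250 mg | 475 mg | 25 mg | 22.6% |
| 10% | 4500 mg | 500 mg | 450 mg | 50 mg | 41.0% |

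If m is instead the fraction of all forms that is missing, and a share q of those reflects infusions truly not given, the rituximab shortfall is 5000 × m × (1 − q). At m = 5% and q = 0.5 it is 125 mg (12.5 mg for IV methylprednisolone). At q = 1 it is zero.

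**4. Consistency check: four forms marked Yes, one missing.**
- Total maintenance rituximab: 4 × 1000 = 4000 mg
- Number of full infusions: 4
- Overall full treatment, text of item 5: Yes, because the missing form is passed over
- Overall full treatment, Table 6 formula: No, because 4 is not 5

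The text and the formula contradict each other whatever the amount of missing data.

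**5. Capture of IV steroid.** Table 2 marks the Follow Up Form at month 24 and at unscheduled visits, but the Treatment Form at neither. Under Protocol 11.6, a first major or second minor relapse before month 24 ends protocolised treatment and the patient passes to local practice. From then on 0 mg is a sound value for protocol pre-medication, but not for IV steroid as a whole. The size of this gap cannot be computed, because the documents give no IV steroid use after relapse.

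**The case against.** Several points stand against the concern.

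- The SAP expects little missing data (8.5), and missing forms are routinely queried (6.4). The 1% to 10% range has no source in the documents, and the full shortfall requires every missing form to hide a complete infusion.
- Zero is correct for protocol dosing after early withdrawal, the first cause that item 5 names. A variable-specific rule may refine the general one in 8.5, so a conflict with 8.5 is a weak argument. The average prednisolone rule is not universal either: the prednisolone AUC in item 6 also takes missing values as 0.
- The Follow Up cumulative doses are reported beside the derived totals, so a reader could notice a discrepancy. The per-visit dose tables will also show how many values are non-missing.
- The totals enter no planned test. Safety is summarised by randomised arm, and the hypogammaglobulinaemia model uses prior treatment, not maintenance dose.

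These points limit the size and the consequence. They do not remove the defect. The Follow Up doses include induction, are described only at 24 months, and come with no reconciliation rule. The per-visit counts do not separate a lost form from a dose not given.

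A reader might infer more: that control patients score 0 mg IV steroid whatever they received, so that the comparison is fixed at about 500 mg against 0 mg. The documents do not support this. It would require that controls have no Treatment Form, or that their IV steroid is not entered on it, and neither is stated. Table 2 does not limit the form to one arm, and SAP 9.10.2 reports its IV methylprednisolone items on the full analysis population. The control-arm effect cannot be computed.

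**Conclusion.** The concern holds for how missing Treatment Forms are scored, and it is a matter of descriptive exposure reporting. Each infusion given but not recorded lowers that patient's rituximab total by 1000 of 5000 mg and the pre-medication total by 100 of 500 mg. The arm-mean shortfall of 50 to 500 mg rituximab rests on an assumed 1% to 10% of given infusions without a form and on full dosing otherwise. It is smaller if some missing forms are true non-administration.

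Two further points need no assumption about missing data. The item 5 text and the Table 6 formula disagree on full treatment. And IV steroid given at a relapse visit, in either arm, may not be counted, because the only source form is not scheduled there. Whether control patients have a Treatment Form is not stated, so no claim about the direction of an arm difference is justified. The primary Cox analysis does not use these totals.

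**What to change.** In SAP 9.2, item 5:

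1. Score 0 mg only when the Treatment Form records non-administration or, for protocol rituximab and its pre-medication, when the planned infusion falls after recorded withdrawal from protocolised treatment. Otherwise treat the form as missing, and report the number by arm.
2. State whether control patients are expected to have a Treatment Form and where their IV steroid is recorded.
3. Keep the Treatment Form total, labelled as protocol exposure, and check it against the Follow Up month 24 cumulative dose.
4. Report a separately labelled all-source total in both arms: Follow Up cumulative dose minus recorded induction doses. Use it for IV methylprednisolone when comparing arms. For rituximab, do not use it to fill gaps in the protocol total: the footnote to SAP 9.10.2 says that Follow Up rituximab includes treatment outside protocol.
5. Make the item 5 text on overall full rituximab treatment agree with the Table 6 formula.

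The cost is SAP wording and a short derivation from data already collected. Some patients will have a missing total, including those without a month 24 Follow Up Form for the all-source figure.
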